1. Laboratory tests: No lab tests will be needed for this study. Study Procedures: We plan to use RedCap electronic data collection tool provided by the University of Kansas Health System. A chart review will be performed to obtain maternal demographic information and secondary outcomes including maternal age, gravity/parity, gestational age at delivery, indication for delivery, mode of delivery, neonatal birthweight, presence of maternal comorbidities such as hypertension, preeclampsia, diabetes, fetal growth restriction, and complications of labor including protracted labor, chorioamnionitis, shoulder dystocia, perineal lacerations, and postpartum hemorrhage. Breastfeeding status at time of postpartum visit will also be collected. This information will be recorded in the RedCap data collection tool. A mixed-methods survey, including eight qualitative and four open ended questions, will be administered by the research coordinator at the postpartum follow-up for both groups. Quantitative questions will assess prenatal, labor and delivery, and postpartum perceived quality of care and satisfaction. Questions will aim to evaluate healthcare communication and perceived quality and respectfulness of care. Qualitative questions will provide the opportunity to comment on the aspect of care that improved the quality of care and contributed to the satisfaction of care. Qualitative responses will be coded to identify common themes. Participants randomized to "Routine Pregnancy Care" will continue to receive routine prenatal care at The University of Kansas and routine pregnancy care during the labor and delivery hospitalization. All postpartum patients at the University of Kansas Health System are screened for postpartum depression using the Edinburgh scale on the day of discharge and at 2 weeks following their delivery by a phone call from a nurse. This will be done for both groups per routine protocol at the University of Kansas Health System. All routine care patients will complete the quantitative survey, have a postpartum follow-up appointment with a provider within 2-6 weeks, and their EHR (Electronic Health Record) will be reviewed to assess the study secondary outcomes. Participants randomized to "Doula Enhanced Care"

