will receive doula care for four visits, two prenatal visits, one labor and delivery visit, and one postpartum visit. When the study patient is admitted for the delivery hospitalization, the Doula will be notified and present for labor and delivery of the participant. The Doula will provide a minimum of one postpartum visit for each study participant. Timeline: Month 1-2: Doula interviews and selection, RedCap data collection tool and survey creation. Make flyers to advertise the study. Month 3-9: Enroll patients and collect data. Month 9-12: Continue to collect data as pregnancies deliver and postpartum visits occur. Chart abstraction and statistical analysis. Doula Enhanced Care participants will have two prenatal visits with a Doula, one labor and delivery visit, and a minimum of one postpartum visit. All postpartum patients at the University of Kansas Health System are screened for postpartum depression using the Edinburgh scale on the day of discharge and at 2 weeks following their delivery by a phone call from a nurse. This will be done for both groups per routine protocol at the University of Kansas Health System. All routine care patients will complete the quantitative survey, have a postpartum follow-up appointment with a provider within 2-6 weeks, and their EHR will be reviewed to assess the study secondary outcomes.

F. Risk/benefit assessment:

1. Physical risk **N/A**
2. Psychological risk **N/A**
3. Social risk **N/A**
4. Economic risk **N/A**
5. Potential benefit of participating in the study
 - a. Benefits of participants with Doula enhanced care may have higher satisfaction and perceived communication and quality of care. They may have lower cesarean delivery, preterm birth, and postpartum depression rates, and higher rates of breastfeeding.
 - b. Benefits of Black birthing people no longer have increased risk of adverse outcomes during pregnancy and childbirth compared to White counterparts.
 - c. The benefit of inequalities between Black and White birthing people may be addressed.

G. Location where study will be performed:

1. Routine Pregnancy Care and Enhanced Doula Care will take place at The University of Kansas Hospital. Surveys will happen at The University of Kansas Hospital and over the phone. Records will be stored in Redcap.

H. Single IRB (Institutional Review Board) Review for a Multi-site study (if applicable):

1. For which sites will KUMC (University of Kansas Medical Center) serve as the IRB of record? **N/A**

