2. Indicate which study activities will occur at each site. If all study procedures will be identical across study sites, state this. **N/A**
3. Describe how you will assess the capacity of each site to perform the research (e.g., expertise, staffing, space, equipment, etc.) If applicable, include site evaluation tools in your IRB submission. **N/A**

4. Describe how the lead investigators will ensure that all participating sites use the IRB-approved version of the protocol, consent, recruitment materials and other study documents. **N/A**
5. Describe how the lead investigators will communicate with and disseminate new information to other sites (e.g., training meetings, regularly scheduled conference calls, notifications, etc.) **N/A**
6. Describe how the lead investigator will assess protocol compliance, unanticipated problems, and adverse events at other sites. **N/A**
7. Name the member of the KUMC study team who will be the point of contact to coordinate oversight and communication with the sites. **N/A**

I. Community-Based Participatory Research

N/A

J. Personnel who will conduct the study, including:

1. Indicate, by title, who will be present during study procedure(s): Routine Pregnancy Care, Doula, PIs (Principal investigators)
2. Primary responsibility for the following activities, for example:
 - a. Determining eligibility: Clinical Research Coordinator
 - b. Obtaining informed consent: Clinical Research Coordinator
 - c. Providing on-going information to the study sponsor and the IRB: Clinical Research Coordinator
 - d. Maintaining participant's research records: Clinical Research Coordinator
 - e. Completing physical examination: Routine Pregnancy Care
 - f. Taking vital signs, height, weight: Routine Pregnancy Care
 - g. Drawing / collecting laboratory specimens: Routine Pregnancy Care
 - h. Performing / conducting tests, procedures, interventions, questionnaires: Routine Pregnancy Care
 - i. Completing study data forms: Clinical Research Coordinator, study team
 - j. Managing study database: Clinical Research Coordinator, study team, PIs, Statistician

K. Assessment of Subject Safety and Development of a Data and Safety Monitoring Plan

1. Elements of the plan include:
 - a. Persons/groups who will review the data (study team; independent safety monitor, data monitoring committee or formal DSMB (Data and Safety Monitoring Board)) The study does not interview with routine pregnancy care, minimal risk only.

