- 2 Clinical Research Coordinator or Investigator will speak directly to the patient either in person or via telephone to explain the study, Doula enhanced care, and discuss interest in enrollment. They will go through the consent form with them, answer questions to satisfaction of the patient, and provide a copy to the patient, as well as contact information should they have questions later
- 3 Only patients able to provide informed consent will be included in this study. Research Coordinator or Investigator will determine if patient is eligible to provide consent. If there is any question to the patient's capacity to give consent, they will consult with the medical team and PI.
- 4 If the PI is the physician responsible for providing direct patient care, to avoid coercion, the patient must be consented by the Clinical Research Coordinator or another Co-Investigator. The care team will not be notified of the patient's enrollment until they participate in study procedures in the office.

D. Alternatives to Participation:

1. Patients may seek Doula enhanced care independent of the study and can be referred to the consulting Doulas assisting in this study.

E. Costs to Subjects:

2. No cost to patient, the grant will pay for the Doula enhanced care.

F. How new information will be conveyed to the study subject and how it will be documented:

3. No new information will be presented to the participants throughout the study. Surveys will be conducted both in person and via phone. Participants answers will be recorded in RedCap.

G. Payment, including a prorated plan for payment:

N/A, part of routine pregnancy care

Payment for a research-related injury:

N/A, part of routine pregnancy care

IV. Data Collection and Protection**A. Data Management and Security:**

1. Participant information will be de-identified by the Clinical Research Coordinator, who will assign an alphanumerical study ID to the patient. Only the Clinical Research Coordinator and PI will have access to identifiable information, which will be stored securely in Redcap and CRIS/Velos systems.
2. All collected data will be stored securely in Redcap or CRIS/Velos systems. There will be no paper source.
3. Subjects will only be identified by an alphanumerical study ID assigned by the Research Coordinator when the survey is conducted.
4. Clinical Research Coordinator and PI will maintain and have access to the key to the assigned groups.

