5. Data will be linked to subjects with an alphanumerical identifier and will only include pertinent PHI (Protected Health Information) for the study.
6. Data will be stored and protected in RedCap
7. Clinical Research Coordinator may consent patients over the phone and with a link to the Redcap survey. Coordinator may use a physical paper copy of the consent, or an iPad provided by KUMC to link directly to the Redcap Survey.
8. No data sent outside KUMC.

B. Procedures to protect subject confidentiality:

1. Data will be kept securely in research databases, password protected, and de-identified. Participants will be assigned a random alphanumerical study ID to associate survey responses with the data.

C. Quality Assurance / Monitoring

1. Self-assessment will be used to assure the data collected are accurate, consistent, complete, and dependable.
2. No plans to have ongoing third-party monitoring.

V.Data Analysis and Reporting

A. Statistical and Data Analysis:

1. The department of OBGYN statistician will perform all statistical analysis. For the primary and secondary outcomes, t-tests will be used to compare continuous variables and chi-squared tests will be used to compare categorical variables. Risk ratios will be computed using simple logistic regression and 95% confidence intervals will be reported. Qualitative questions will be coded, and common themes will be identified.

B. Outcome:

1. Our primary objective is to demonstrate improved perceived communication and quality of maternal care among Black birthing people with enhanced Doula enhanced care compared to routine pregnancy care at the University of Kansas Health System. We will use quantitative surveys to assess satisfaction and perceived quality of prenatal, labor and delivery and early postpartum care.

C. Study results to participants: Participants will receive a letter with the study results.

D. Publication Plan: If successful in improving pregnancy care with an increase in perceived quality of care and reduction adverse pregnancy outcomes, we will use our results to write a pilot study and submit a poster or abstract for ACOG or SMFM.

VI. Bibliography / References / Literature Cited

Reference:

1. Society for Maternal-Fetal Medicine and National Birth Equity Collaborative infographic, Strategies to Overcome Racism's Impact on Pregnancy Outcomes." Accessed June 16, 2022 at: https://s3.amazonaws.com/cdn.smfm.org/media/2315/Strategies_to_Overcome_Racism_Infographic.pdf.

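### The subjective primary survey is administered by a coordinator with access to the allocation key, with no rule on phone or in-person mode; self-completion would reduce, but not remove, the resulting reporting bias

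*Combined protocol and SAP*

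**What the plan says.** **Outcome.** Section V.B defines the primary measure: "We will use quantitative surveys to assess satisfaction and perceived quality of prenatal, labor and delivery and early postpartum care". Section II.E adds that the questions cover communication and respectful care. Every component is the patient's own judgement.

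**Who gives it.** Section II.E says the survey "will be administered by the research coordinator at the postpartum follow-up for both groups". The list of responsibilities in II.J.2.h reads "Performing / conducting tests, procedures, interventions, questionnaires: Routine Pregnancy Care". II.J.1, on who is present at study procedures, names routine pregnancy care, the doula and the PIs, but not the coordinator.

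**Knowledge of the arm.** Section IV.A.4: "Clinical Research Coordinator and PI will maintain and have access to the key to the assigned groups". No blinding of the person giving the survey is described. Under II.J.2 the coordinator also determines eligibility and obtains consent, although III.C lets investigators obtain consent too.

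**Mode.** Section II.G: "Surveys will happen at The University of Kansas Hospital and over the phone". Section III.F: "Surveys will be conducted both in person and via phone". Neither says which patients are surveyed in which way.

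**Electronic completion.** Section IV.A.7: "Clinical Research Coordinator may consent patients over the phone and with a link to the Redcap survey". The same item mentions an institutional iPad that opens the REDCap survey. Both appear in the context of consent; neither is stated to be how the outcome survey is completed.

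**The concern.** Ratings of satisfaction, communication and respect respond readily to who asks and how. A patient interviewed by someone who knows her arm may be prompted differently, or may give the answer she thinks is wanted. A patient asked by the service she is rating may be reluctant to criticise it. If such effects differ between arms, they enter the primary difference at full size, and the planned t-test cannot separate them from an effect of doula care.

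The protocol already recognises this kind of pressure at consent: III.C.4 stops a PI who is treating a patient from consenting her. There is no matching safeguard at the survey, where the patient rates that care. Section I.B says that a successful result would support a larger grant proposal, so a biased difference would carry forward.

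**Working it through.** **1. The sections side by side**

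- II.E is the only text specific to this survey. It names one administrator and one occasion, the same in both arms.
- IV.A.4 shows that this administrator has access to the allocation. IV.A.3 identifies patients by study ID at the survey, but the coordinator assigns the ID, so this does not blind the coordinator.
- II.J.2.h gives questionnaires to routine pregnancy care. Read literally, that conflicts with II.E.
- II.G and III.F allow two modes. No section assigns the mode, fixes it across arms or asks for it to be recorded.
- Exclusion criterion II.D.2.b requires patients to accept possible assignment to no doula, and the doula attends in person. Patients therefore know their arm, whoever gives the survey.

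**2. Illustration of size**

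The plan has no figure of its own to reproduce on this point. Inputs from the documents: 20 patients per arm (II.C.2) and t-tests for continuous outcomes (V.A). Assumptions: a continuous survey score, two-sided alpha of 0.05 (consistent with the 95% intervals in V.A), no true effect, and a purely artefactual shift of b SD in favour of doula care.

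- Degrees of freedom: 2 × 20 − 2 = 38; critical value 2.024.
- Standard error of the difference: √(2/20) = 0.316 SD.
- Noncentrality: δ = b × √(20/2) = b × 3.162.
- Rejection probability: P(T > 2.024) + P(T < −2.024), with T noncentral t on 38 df and noncentrality δ.

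| Assumed shift b (SD) | δ | Rejection probability |
|---|---|---|
| 0 | 0 | 5.0% |
| 0.1 | 0.316 | 6.1% |
| 0.15 | 0.474 | 7.5% |
| 0.2 | 0.632 | 9.5% |
| 0.3 | 0.949 | 15.2% |

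At b = 0.2, 8.96% of trials would be significant in favour of doula care and 0.50% against it. At b = 0.3 the split is 15.03% and 0.20%. The excess is almost all in the direction the study hopes to show.

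**3. What self-completion could gain**

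Suppose, again as an assumption, that it removed half of the shift. Then 0.2 becomes 0.1 and 0.3 becomes 0.15, so the rate falls from 9.5% to 6.1%, or from 15.2% to 7.5%. It returns to 5% only if the whole shift disappears.

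**The case against.** The case on the other side is substantial.

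- **The care-team line is generic.** A reader might infer from II.J.2.h that the rated staff collect the primary outcome. The documents do not support that. The list is a template; item g even assigns laboratory specimens, although II.E says the study needs no laboratory tests. The word questionnaires could mean routine instruments such as the nurse-administered Edinburgh scale, and the text specific to this survey names the coordinator. This stands: the line is an ambiguity to reconcile, not proof.
- **No difference between arms is shown.** A reader might infer that mode or timing differs by arm, partly because the 2-6 week appointment is written only for routine-care patients. That phrase describes a provider visit, not a survey window, and II.E ties the survey to postpartum follow-up in both groups. Mixed mode that is balanced across arms mainly adds noise. This also stands; what remains is that nothing prevents or records an imbalance.
- **Answers may not be spoken.** Phone surveys imply spoken answers, but in-person completion might already be on a device. The text does not say, so this limits the concern without answering it.
- **The remedy has trade-offs.** A link with a phone fallback is still mixed mode, and non-response could differ by arm. Low health literacy and financial strain are among the screening domains in III.A.2, so non-response to a link should be expected. This is why the iPad at the visit should be the default and mode should be reported by arm.

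The objection does not reach the central fact: a subjective primary outcome is administered by someone with access to the allocation, although the protocol already mentions tools for another method.

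**Conclusion.** The point holds as an avoidable weakness in how the primary outcome is collected. The subjective outcome, the coordinator's access to the key and the absence of a mode rule are all in the text. The conflict between II.E and II.J.2.h is one of wording and needs to be reconciled.

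It should not be read as saying that self-completion would make the comparison unbiased. It takes away the interviewer's influence, but expectation or gratitude from knowing one's own arm remains.

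Nor is 9.5% to 15.2% an estimate of this trial's error rate. It rests on an assumed shift of 0.2 to 0.3 SD, a continuous score and a two-sided 5% test. The documents give no scale, SD or alpha, and no evidence that a shift of that size, or any shift, would occur. The change is worth making because it is cheap and the outcome is vulnerable, not because a bias has been measured.

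**What to change.** - **II.E:** have patients in both arms complete the closed-ended items themselves in REDCap, by default on the clinic iPad at the postpartum follow-up, or by link if they do not attend. Use the same window and reminders in both arms, with no care-team member or doula present.
- **II.E, II.G and III.F:** restrict phone completion to non-responders. Use a script, and have the call made by existing study staff outside the care team, where possible without access to the key. Record mode and timing, and report both by arm.
- **Open-ended items:** the coordinator may still ask these once the closed-ended answers have been submitted.
- **II.J.2.h:** reconcile with II.E so that the care team does not administer the study survey, and clarify which questionnaires the line covers.

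**Cost:** a REDCap form setting and edits to these sections. Sample size, treatment and staffing do not change. The downsides are some non-response to the link, partly covered by the phone call, and possibly briefer open-ended answers if those are also self-completed.

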2. By better understanding if Doula enhanced care improves communication and quality of maternal care, we can begin to understand how to improve maternal care for Black birthing people. Also, by having Doula enhanced care available, we might reduce the chances of cesarean delivery and preterm birth and increase the likelihood of breastfeeding.

II. Research Plan and Design

A. Study Objectives:

1. The primary objective of the study is to demonstrate improved perceived communication and quality of maternal care among Black birthing people with Doula enhanced care compared to routine pregnancy care at the University of Kansas Health System. This study's primary outcome is to provide evidence that Doula enhanced care improves communication and satisfaction for Black-birthing people by improving the quality of healthcare with the addition of Doula enhancement to the health care team. In addition, the secondary outcome is to show how Doula enhanced care will improve specific disparities between Black birthing people and their White counterparts, including cesarean delivery, preterm birth, postpartum depression, and breastfeeding rates.

B. Study Type and Design:

This study will be an interventional randomized control trial that will have a control group and an experimental group. These groups will be randomly assigned at the patient's enrollment into the study.

C. Sample size, statistical methods, and power calculation

1. Two test Run patients will receive Doula Care from [name]. This will consist of two prenatal visits.
2. Randomization will be 1:1 and will stop after reaching our desired sample size of forty total patients. Forty patients will be enrolled in the study. Twenty patients will receive Doula enhanced care and Twenty patients will receive routine pregnancy care.

D. Subject Criteria (See Vulnerable Populations appendix, if applicable):

1. Inclusion criteria:

- a. Black birthing people receiving prenatal care with planned delivery at University of Kansas Health System between the ages of 16 and 50 years old.
 - i. Parental consent is not required for minors less than 18 years old because this study is directly related to their pregnancy.
- b. A positive social determinants of health screen.

- c. Patients must have an estimated gestational age of at least 14 weeks, but less than 28 weeks (27.6) when enrolled in the study.

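### The 12-month timeline is too short for the follow-up of everyone it allows to enroll: the last primary-outcome survey could fall at about month 14.4 to 16.4.

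*Combined protocol and SAP*

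**What the plan says.** Section II.E.1 of the protocol sets out the calendar. Months 1-2 are for set-up. Then: "Month 3-9: Enroll patients and collect data. Month 9-12: Continue to collect data as pregnancies deliver and postpartum visits occur". The next item, still inside months 9-12, is: "Chart abstraction and statistical analysis". Month 9 appears in both phases, so it is unclear whether enrollment includes that month or stops as it begins.

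Three other statements fix how long each participant must be followed:

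- Inclusion criterion II.D.1.c: "Patients must have an estimated gestational age of at least 14 weeks, but less than 28 weeks (27.6) when enrolled in the study".
- Survey timing, II.E.1: the mixed-methods survey "will be administered by the research coordinator at the postpartum follow-up for both groups".
- Visit timing, II.E.1: routine-care patients "have a postpartum follow-up appointment with a provider within 2-6 weeks". No separate window is given for the doula arm.

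Section II.C.2 stops randomization once 40 patients (20 per arm) are in. The protocol gives no expected accrual rate, no distribution of gestation at entry, no date or event for database lock, and no rule for participants still pregnant or not yet surveyed when the analysis is run.

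**The concern.** The primary outcome, perceived communication and quality of care, does not exist for a participant until her postpartum survey. Breastfeeding status is collected at the same visit. If the pregnancies and postpartum intervals do not fit between enrollment and month 12, an analysis run on the stated schedule covers a partial cohort. With 20 per arm, each missing survey matters.

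A calendar cut would also select on pregnancy length, since short pregnancies finish sooner. Preterm birth is a named secondary outcome, so the possible distortion needs to be sized as well as the loss.

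**Working it through.** **Inputs from the protocol.** Enrollment months 3-9, end of timeline month 12 (II.E.1); entry at 14w0d to 27w6d, that is 14 to 27.86 weeks (II.D.1.c); postpartum visit at 2 to 6 weeks and survey at that visit (II.E.1); 40 participants (II.C.2).

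**Conventions and assumptions.** Time t is elapsed months, so month 12 ends at t = 12. Enrollment opens at t = 2 and closes at t = 9 (month 9 included) or t = 8 (stops as month 9 starts). One month is 365.25/12/7 = 4.348 weeks. Delivery at 40 weeks is an assumption for the calendar check; each week earlier takes off 0.23 months.

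**The plan's own figure.** The protocol shows no derivation of the 12 months. Its months leave 12 − 9 = 3 months (13.0 weeks) or 12 − 8 = 4 months (17.4 weeks) after the last enrollment, with nothing set aside for analysis.

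**Time needed.** Months from entry to survey = (delivery week − entry week + postpartum weeks) / 4.348.

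| Entry | Visit | Weeks | Months | Finish if enrolled at t = 9 | Finish if enrolled at t = 8 |
|---|---|---|---|---|---|
| 14w0d | 2 weeks | 40 − 14 + 2 = 28 | 6.44 | 15.44 | 14.44 |
| 14w0d | 6 weeks | 40 − 14 + 6 = 32 | 7.36 | 16.36 | 15.36 |
| 27w6d | 2 weeks | 40 − 27.86 + 2 = 14.14 | 3.25 | 12.25 | 11.25 |
| 27w6d | 6 weeks | 40 − 27.86 + 6 = 18.14 | 4.17 | 13.17 | 12.17 |

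A late-enrolled 14-week entrant overruns month 12 by 2.4 to 4.4 months on either reading of month 9. With enrollment at t = 8, a 40-week delivery and a 2-week visit, only entry at 42 − 17.4 = 24.6 weeks or later fits.

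**Share without a survey if the data were cut at the end of month 12.** This needs assumptions that are not in the protocol: accrual uniform from t = 2, entry gestation uniform, 15% preterm (delivery uniform over 30-37 weeks), the rest uniform over 37-41 weeks, visit uniform over 2-6 weeks. Simulation with 2 million draws, rerun for this point:

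| Accrual ends at | No survey by month 12 | Of 40 |
|---|---|---|
| t = 5 | about 0% | 0 |
| t = 6 | 2% | 1 |
| t = 7 | 8% | 3 |
| t = 8 | 17% | 7 |
| t = 9 | 27% | 11 |

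Visit timing moves the last two rows to 11-23% and 21-34% (all visits at 2 weeks, or all at 6). With every delivery fixed at 39 or 40 weeks, the uniform case gives 13-40% over both readings of month 9. Skewed entry gestation widens that to 6-47%, and front- or back-loaded accrual with visits spread over 2-6 weeks gives 6-53%.

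**Preterm share under the same cut.** With a true 15%, the share among those surveyed by month 12 is 16.1% (accrual to t = 7), 17.1% (t = 8) or 17.8% (t = 9), an excess of about 1 to 3 points. Gestational age at delivery comes from chart review (II.E.1), so the relevant group is everyone delivered: 15.9% (t = 8) or 16.7% (t = 9). Even 17.8% against 15% among 29 surveyed is 0.028 × 29 = 0.8 of one birth, against a standard error of √(0.15 × 0.85/29) = 6.6 points.

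**The case against.** The strongest reply is that the timeline is a list of planned activities and not a data cut. Nothing in the protocol calls month 12 a lock, proposes to analyse a partial cohort, or says unsurveyed participants are dropped. If follow-up simply runs late, nobody is lost and nothing is biased. Accrual also stops at 40, and if it ends by t = 5 or 6 the problem nearly disappears. Both points stand, and they make the loss conditional. They do not rescue the calendar. The plan itself allots enrollment up to month 9, gives no accrual rate to support an earlier finish, and places statistical analysis inside months 9-12. Telephone surveys do not help either: "Surveys will happen at The University of Kansas Hospital and over the phone", but a call still has to wait for the birth.

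Three stronger readings are tempting and are not supported:

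- *About a quarter of participants will lack a survey.* That needs a month-12 cut, accrual spread evenly through month 9, and uniform entry gestation. The protocol states none of these.
- *Nobody enrolled at the end of the window can finish in time.* This is false if enrollment ends as month 9 starts (27w6d entry, 40-week delivery and 2-week visit finish at 11.25). It is also false at t = 9 with a 38-week delivery: 9 + (38 − 27.86 + 2)/4.348 = 11.8.
- *The cut would bias the comparison or materially inflate preterm birth.* Both arms are randomised concurrently and surveyed at the same follow-up, so the same truncation applies to each. A between-arm difference would need doula care to change gestational age at delivery. The protocol hypothesises that effect, but no resulting bias has been shown. The shift in the preterm rate is trivial at this sample size.

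**Conclusion.** The calendar conflict is established from the protocol's own enrollment months, entry criterion and visit window, together with a 40-week delivery, and it holds on either reading of month 9. Keeping to the stated months for analysis would mean analysing before all permitted participants have a primary outcome.

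The size of any loss is not established. About 17% to 27% of participants without the survey is a fair central figure for uniform accrual over the full window and a month-12 analysis. It falls to 0-8% with accrual finished by t = 5 to 7, and the range is wider under other accrual, gestation and visit-timing assumptions. Preterm over-representation is a minor side effect of such a cut and not a reason for the change.

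**What to change.** Reconcile the timeline in II.E.1 with the entry criterion in II.D.1.c and the postpartum visit window in II.E.1. In section V.A, tie the lock to an event, for example: *Database lock and all comparative analyses take place after the postpartum survey of the last randomised participant, or after that participant's survey window has closed.* Say whether enrollment includes month 9, and state the survey window for both arms.

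Then restate the timeline: follow-up to about month 16.4 if enrollment runs through month 9, or about 15.4 if it ends as month 9 starts, with time for chart abstraction and analysis added after that.

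If month 12 proves to be a fixed end, which the protocol does not say, the alternative is to close entry by expected due date. Allowing for a 40-week delivery and a 6-week visit, that means about t = 12 − 7.36 = 4.6 for entry at 14 weeks and t = 12 − 4.17 = 7.8 for entry at 27w6d, at the price of a shorter recruitment window.

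The event-based lock costs a later finish and a protocol amendment. It needs no extra patients.
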